#### *11.2.7 Reporting of All Other Adverse Events*

For any and all adverse events, study coordinators and/or Principal Investigators will use the standard procedure of documenting the event using the Adverse Events Case Report Form.

Six months after the first subject is enrolled in the study, and at the end of each 6 months thereafter, the SDMC will:

- Use the current version of the MedDRA dictionary to code all AEs that have been recorded on study AE forms.
- Make a “snapshot” copy of the adverse events data, including MedDRA codes.
- Create frequency tables of treatment x occurrence (yes or no, since inception of the study) of all patients. One table will be created for each highest level MedDRA term for which AEs have been reported. The counting units are patients, not events.
- Compute Fisher’s Exact Test (FET) statistic to test the alternative hypothesis that occurrence of AEs is not independent of treatment group. The FET p-value is not adjusted for multiplicity.
- If the FET p-value is less than the critical value shown in Table 3 and the active treatment group has a higher AE rate, the SDMC will conduct further statistical analyses as indicated by the circumstances and alert the DSMB to this finding in the semi-annual DSMB report.
- Collaborate with the Principal Investigator to incorporate the results into the study’s semi-annual report to the DSMB and the NHLBI Project Officer.

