## 11.2 Adverse Events

### 11.2.1 Definitions of Adverse Events and Serious Adverse Events

An adverse event (AE) is defined for this study as any untoward medical occurrence in a patient or clinical investigation subject administered a pharmaceutical product that does not necessarily have a causal relationship with this treatment. An AE can therefore be any unfavorable and unintended sign (including an abnormal laboratory finding), symptom, or disease temporally associated with the use of a medicinal (investigational) product, whether or not related to the medicinal (investigational) product. AE data are recorded on the CRF form.

A serious adverse event (SAE) is defined as any untoward medical occurrence that at any dose:

- Results in death;
- Is life-threatening (i.e. an event in which the subject was at risk of death at the time of the event; it does not refer to an event which hypothetically might have caused death if it were more severe).
- Requires inpatient hospitalization or prolongation of existing hospitalization.
- Results in persistent or significant disability/incapacity.
- Results in a congenital anomaly/birth defect.
- In the opinion of the investigator, important medical events that may not be immediately life-threatening or result in death or hospitalization but may jeopardize the subject or may require intervention to prevent one of the other outcomes listed in the definition above, may be considered serious. Examples of such events are intensive treatment in an emergency room or at home for allergic bronchospasm; blood dyscrasias or convulsions that do not result in hospitalization; or development of drug dependency or drug abuse.

An *expected SAE* for subjects in this study is an adverse event that is listed in Table 11.1 and is a serious adverse event, as defined above. An *unexpected SAE* for subjects in this study is any AE that is **not** listed in Table 11.1 and is a serious adverse event, as defined above.

Table 11.1. List of Expected Adverse Events in This Study

Expected AE	Expected AE	Expected AE
Acute chest syndrome	Pyelonephritis	Hypoxemia (PO 2 < 65mm Hg)
Anemia	Renal failure	Infection, pneumococcal
Aplastic crisis	Renal insufficiency/albuminuria	Jaundice
Aplastic crisis/anemia	Renal papillary necrosis	Leukocytosis
Arthralgia	Reticulocytosis (≥10%–20%)	Meningitis
Avascular necrosis of hip/shoulder	Retinal disease	Rhabdomyolysis
Avascular necrosis of the femoral head	Retinal hemorrhage	Sepsis

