#### *11.2.4 Reporting of Adverse Events*

Serious safety issues that arise in this study will be brought to the attention of the CSCC Data and Safety Monitoring Board (the “DSMB”), which will make recommendations to the NHLBI regarding possible suspension of the study. The NHLBI will consider the DSMB’s recommendations, determine an appropriate action and notify the Principal Investigator and the CSCC Statistics and Data Management Center (SDMC). The Principal Investigator will notify all participating investigators, who will implement the actions directed by NHLBI. This section defines “serious safety issues” and describes procedures for bringing them to the attention of the DSMB.

This study is being conducted under an Investigational New Drug Application (“IND”). Consequently, U.S. Government regulations require that all “unexpected serious adverse events” (defined below) must be reported to the Food and Drug Administration (FDA) within either 7 calendar days (fatal or life-threatening events) or 15 calendar days (non-fatal, non-life-threatening). These Suspension Guidelines require that unexpected serious adverse events also be reported to the DSMB within the same timeframe. The FDA has the authority to direct the investigators to suspend or terminate the study, or take other actions.

These Guidelines specify the following types of reports that can alert the DSMB to a potential safety issue:

- Ad hoc reports of unexpected serious adverse events that are made within 7 or 14 calendar days, as specified in subsequent paragraphs.
- Reports of quarterly statistical analyses of all serious adverse events. The SDMC makes such analyses quarterly, but files a report to the DSMB only when analyses indicate that a safety issue has arisen, as defined by the “alert” criteria.

Semi-annual DSMB reports of analyses of adverse events and of clinical laboratory results. These reports will highlight any safety issues revealed by the analyses that meet the “alert” criteria.

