#### *11.2.6 Reporting of Expected Serious Adverse Events*

Within 3 days of the realization that an expected SAE has occurred to a study subject, a study investigator must make an initial report:

- To the Principal Investigator
- To the CSCC Statistics and Data Management Center SAE Regulatory Specialist

The investigator must also report the expected SAE to the site's IRB in accordance with the IRB's regulations or procedures.

Three months after the first subject is enrolled in the study, and at the end of each 3 months thereafter, if any SAEs (expected or unexpected) have been reported in the study during the preceding 3 months, the SDMC will:

- Use the current version of the MedDRA dictionary to code all AEs (serious or not) that have been recorded on study AE forms.
- Make a “snapshot” copy of the adverse events data, including MedDRA codes.
- Create frequency tables of treatment x occurrence (yes or no, since inception of the study) of all patients. One table will be created for each highest level MedDRA term for which SAEs have been reported. The counting units are patients, not events.
- Compute Fisher’s Exact Test (FET) statistic to test the alternative hypothesis that occurrence of SAEs is not independent of treatment group. The FET p-value is not adjusted for multiplicity.
- If the FET p-value is less than the critical value shown in Table 3 and the active treatment group has a higher AE rate, the SDMC will conduct further statistical analyses as indicated by the circumstances and report the results to the Chair of the DSMB subcommittee monitoring this study, the Principal Investigator, and the NHLBI Project Officer.
- The SDMC will not file a report of expected SAEs if none of the FET p-values is less than the critical value shown in Table 3 or if the relative risk is less than 1.

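### The safety alert tests only one yes/no table per highest-level MedDRA term, so sickle-cell background events can mask a specific moderate-to-large toxicity in the same class

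*Protocol*

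**What the plan says.** Section 11.2.7 (all AEs, every six months) specifies: "One table will be created for each highest level MedDRA term for which AEs have been reported. The counting units are patients, not events". Occurrence is yes or no since study inception, and Fisher's exact test is used to "test the alternative hypothesis that occurrence of AEs is not independent of treatment group", without adjustment for multiplicity. An alert needs p below the critical value and a higher rate on active treatment. Table 11.3 sets that value at p<0.01 (the text calls it Table 3).

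Section 11.2.6 applies the same construction to SAEs each quarter: "One table will be created for each highest level MedDRA term for which SAEs have been reported". Here a non-significant result stops the report: "The SDMC will not file a report of expected SAEs if none of the FET p-values is less than the critical value". Section 11.2.4 describes this quarterly analysis the same way: the data centre "files a report to the DSMB only when analyses indicate that a safety issue has arisen", with the alert criteria defining such an issue.

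No table below the highest level enters either alert rule. Section 11.2.1 defines an AE broadly, to include "any unfavorable and unintended sign (including an abnormal laboratory finding), symptom, or disease". Table 11.1 lists expected disease events across many organ systems.

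**The concern.** The highest MedDRA level is taken here to be the system organ class. In this population many patients are likely to have a disease-related event in some classes whatever they are given. Once such a patient is scored yes, a further drug-related event in the same class changes nothing in the table.

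The protocol supplies an example. Section 5.6 names gastrointestinal upset and headache as the effects reported with long-term oral arginine, while Table 11.1 lists severe abdominal pain as an expected background event. Among SAEs, an excess of pulmonary embolism could be hidden by acute chest syndrome if the two are coded to the same class. Both are in Table 11.1, so as SAEs both count as expected.

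At stake is whether the alert responds to a specific excess that a finer table from the same coded data would show.

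**Working it through.** The protocol states no operating characteristics for the alert, so there is no figure to reproduce.

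**Inputs from the protocol**
- Arm size: 16 per arm per age group (section 7.2), so 16 + 16 = 32 low dose and 32 placebo with ages pooled.
- Former high-dose patients: 16 + 14 = 30 (section 7.2), so 32 + 30 = 62 active if doses are pooled. The alert text does not say whether doses or ages are pooled.
- Rule: two-sided Fisher p<0.01 and a higher active rate (section 11.2.7, Table 11.3).

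**Assumptions**
- A specific term rises from 5% on placebo to 35% on active.
- Other events in its class affect a proportion b of patients in both arms, independently of that term.

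**Formulas**
- Class rate = 1 − (1 − term rate)(1 − b). At b = 40%: placebo 1 − 0.95 × 0.60 = 43%; active 1 − 0.65 × 0.60 = 61%.
- Alert probability = the sum, over all pairs of counts meeting the rule, of the product of the two binomial probabilities (exact enumeration).

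**Results, 32 against 32**

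| Background b | Placebo class rate | Active class rate | Alert probability |
|---|---|---|---|
| 0 (term alone) | 5% | 35% | 59% |
| 5% | 9.75% | 38.25% | 44% |
| 10% | 14.5% | 41.5% | 34% |
| 20% | 24% | 48% | 21% |
| 40% | 43% | 61% | 8% |
| 60% | 62% | 74% | 4% |
| 80% | 81% | 87% | 1% |

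With 62 against 32, the probability is 81% for the term alone and 17% at b = 40%. Earlier looks have fewer patients, so these are full-enrolment figures.

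**Ceiling (no assumed effect size).** Let all 32 active patients have an event in the class. If 25 of 32 placebo patients also do, the 7 non-events all lie on placebo, and two-sided p = 2 × C(32,7)/C(64,7) = 0.0108: no alert. With 24 placebo patients, p = 2 × C(32,8)/C(64,8) = 0.0048: alert. So at 25 or more placebo patients (78%) no result can alert. With 62 active the corresponding limit is 28 of 32.

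**Small toxicities.** A rise from 5% to 15% alerts with probability 2.4% for the term alone, 1.6% at b = 20% and 0.9% at b = 40%. Aggregation is not the main cause there.

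**Plausibility of the range.** The nearest figure in the protocol is in section 12.1: at least 24 vaso-occlusive pain events per age group. For 48 children that is 24/48 = 0.5 per patient. If the events followed a Poisson distribution and were coded to one class, 1 − e^(−0.5) = 39% of patients would have one. The period and coding are not stated, so this is only a rough guide to one class.

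**The case against.** The strongest reply is that the alert is one layer among several.
- Under section 11.2.7 the results go into the semi-annual DSMB report whether or not an alert fires, and Table 11.3 confirms this.
- Unexpected SAEs are reported case by case with no test (section 11.2.5).
- Section 11.2.8 has its own alert for each laboratory measure, so a drug effect on laboratory values does not depend on a class table.
- The DSMB examines unblinded safety data and may recommend stopping at any time (section 13.1).
- Expected SAEs still go to the Principal Investigator and the data centre within 3 days. They are also recorded as AEs, so they enter the six-monthly analysis.

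All of this stands. A reader might infer that the protocol treats no alert as no safety issue throughout. The text supports that only for the quarterly expected-SAE analysis, and even there an additional report is withheld, not the data.

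A reader might also infer that aggregation makes the test miss most real harms. That is not supported either. In classes with little background a large excess is often detected, and small ones are missed at any level because of arm size and the 0.01 threshold.

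Two further points have weight. SAE tables exclude non-serious laboratory findings and similar events, so their class backgrounds may lie at the low end of the range. Class tables can also outperform term tables: if the 5% to 35% excess splits equally over three independent terms, the chance that any of them alerts is about 10%, against 21% at class level with 20% background. That argues for keeping the class tables, not for using them alone.

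**Conclusion.** The point holds as a weakness in how the alert is built. It is neither a contradiction in the protocol nor a failure of safety oversight. For a 30-percentage-point rise in one term, sensitivity at 32 against 32 falls from 59% to between 44% and 1% as class background goes from 5% to 80%, and an alert becomes impossible at 25 of 32 placebo patients. The loss matters most for expected SAEs each quarter, where the test decides whether a report is filed. For all AEs it costs the flag and the further analyses that the flag triggers.

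The percentages rest on assumed background and effect rates, independence between the term and the background, pooled age groups and full enrolment. The ceiling depends only on arm size and the stated rule.

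**What to change.** In sections 11.2.6 and 11.2.7 and Table 11.3, keep the class-level tables and add the same patient-level table, test and alert at MedDRA preferred-term level. File the expected-SAE report, or raise the AE alert, when either level meets the criterion.

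The cost is wording in three places and some extra programming, since every AE is already MedDRA-coded. There will be a few more chance alerts. With equal true rates in both arms at 32 against 32, the chance per table is about 0.05% at a 10% event rate and peaks at about 0.25%. At 62 against 32 it stays below 0.5%. Rare terms cannot alert by chance at all: with no placebo cases, at least 8 of 32 active patients are needed. As an illustration, 100 terms each at 10% in both arms would give 100 × 0.0005 = 0.05 expected chance alerts per look.

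The change does not help with small toxicities, which the arm size and threshold leave undetected.

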### 11.2.8 Reporting of Safety Laboratory Measures

Six months after the first subject is enrolled in the study, and at the end of each 6 months thereafter, the SDMC will:

- Make a “snapshot” copy of the study’s clinical laboratory data.
- Perform an appropriate statistical analysis of clinical laboratory change-from-baseline data for each clinical laboratory evaluation obtained in this study.
- Perform an appropriate statistical test of:  $H_0$ : The mean (or median, or proportion, as appropriate) change-from-baseline of the clinical laboratory values for the active treatment group is the same as for the placebo group, vs.  $H_a$ : The mean (or median, or proportion) change-from-baseline in the active treatment group is “worse” than for the placebo group. The meaning of “worse” depends upon the specific clinical lab measurement. The test statistic p-value is not adjusted for multiplicity.
- If the hypothesis test p-value is less than the critical value shown in Table 3, the SDMC will conduct further statistical analyses as indicated by the circumstances and highlight this finding in the semi-annual DSMB report.
- Collaborate with the Principal Investigator to incorporate the results into the study’s semi-annual report to the DSMB and the NHLBI Project Officer.

Table 11.3. Summary of Procedures and Timing for Alerting the DSMB and NHLBI Project Officer of Possible Serious Safety Issues

Situation or Event	Summary of Procedure (See text for details.)	Critical Value for DSMB “Alert”
Unexpected SAE	1. Site investigator notifies SDMC SAE Regulatory Specialist and Principal Investigator within 8 hours.	Alert all cases.
	2. Site investigator, SDMC SAE Regulatory Specialist and Principal Investigator prepare report using FDA forms and submit report to DSMB, NHLBI Project Officer, IRBs, study investigators. Report: 1. Fatal or life-threatening: within 7 calendar days. 2. Otherwise: within 14 calendar days.	Alert all cases.
Expected SAE	SDMC performs quarterly analyses of MedDRA-coded SAEs, tabulates patients with SAEs classified by highest level MedDRA term. Report only when $p <$ critical value and active treatment group has higher AE rate.	$p < 0.01$ $p$ not adjusted for multiplicity
Adverse Events (all)	SDMC performs semi-annual analyses of MedDRA-coded AEs, tabulates patients with AEs classified by highest level MedDRA term. Report every 6 months. Alert only when FET $p <$ critical value and active treatment group has higher AE rate.	$p < 0.01$ $p$ not adjusted for multiplicity
Adverse	SDMC performs semi-annual analyses of clinical lab	$p < 0.005$

Clinical Lab Results	change-from baseline using analyses appropriate for the data type. Report every 6 months. Alert only when $p < \text{critical value}$ and change is in “adverse” direction.	p not adjusted for multiplicity
----------------------	---	---------------------------------

### 11.2.9 Subject Discontinuation due to Adverse Event(s)

The following criteria will be used to determine whether or not specific subjects exhibit toxicities of the study drug(s) sufficient to require discontinuation from the study.

While oral arginine has been shown to have little toxicity when given in the doses outlined in this study, we will closely monitor signs, symptoms, and laboratory findings to assess for unexpected toxicities. Arginine will be discontinued in any patient who experiences the following:

- Drop in hemoglobin below 5gm/dL
- Pulmonary failure requiring intubation
- Hepatic dysfunction (SGPT  $\geq 3X$  normal and albumin  $\leq 3.0$ )
- Renal dysfunction (Creatinine  $\geq 1.4$  for children and  $\geq 1.6$  for adults)
- Focal neurological changes
- Increase in methemoglobin level to  $>2X$  normal level
- Apparent allergic reaction to arginine
- Severe headache
- Pregnancy

*In addition, patients will also have arginine discontinued if they become unable to orally ingest arginine or at the request of the patient for any reason. In the event that arginine is stopped, patients will continue to be followed by study personnel to assess for potential side effects of arginine administration.*

### 11.2.10 Pregnancy Testing

Arginine is not expected to have any significant toxicity in pregnant patients, however, it is unknown what the effect of pregnancy on NO and vascular biology will be. For this reason, pregnant patients will be excluded from the study. Female subjects who are pubertal will be regularly assessed for pregnancy throughout the study. In the event of a test indicating the study subject is pregnant they will be informed of this result and will immediately have arginine discontinued.

## 11.3 Data Collection and Data Monitoring

### 11.3.1 CRF and Source Documentation

The site study coordinator will complete a case report form (CRF) for each subject. A CRF manual will be provided to each site to assist in correct CRF completion. Study

participants must not be identified by name on any study documents. Subjects will be assigned and identified by CSCC subject numbers assigned at enrollment.

### *11.3.2 Data Management*

The SDMC will provide statistical and data management support for the study. Validation rules will be applied at several points in the data management process. An error correction procedure will be applied to correct data values that fail validation rules.

### *11.3.3 Data Monitoring*

After study initiation, individual sites will monitor CRFs and source documents for accuracy, protocol compliance, subject safety, and adherence to guidelines outlined in the CSCC Manual of Procedures. A member of the SDMC will visit the site to assess data quality at least once annually.

### *11.3.4 Reporting Protocol Violations*

All protocol violations and deviations will be reported as soon as possible using the SDMC Deviation/Violation Form. This form will ask for a description of the event and what corrective action is planned.

## 12 STATISTICAL ANALYSIS

### 12.1 Sample Size

A total of 94 patients will be enrolled into this trial over an 18-month period (48 children and 46 adults). It is estimated that 6 to 8 clinical centers (12-16 patients per center) will be required to enroll sufficient patients in this period.

Initially, subjects were randomized to one of three treatment groups: placebo, low dose arginine and high dose arginine. With this amendment, subjects are now only randomized to placebo and low dose arginine. Subjects will be stratified by age group (5-17 years,  $\geq 18$  years) and since there could be drastic differences between these groups, they will be analyzed separately. Thus, all sample size calculations will be for each of these two groups.

We have identified three measurements that are of primary interest: Nitric Oxide, Gardos Channel Activity, and erythrocyte density (MCHC  $>41$ ). We will measure our panel of investigative laboratory measures at various time points between baseline and sixteen weeks (up to eight timepoints). In order to avoid making more assumptions than necessary for our sample size calculations, we will use a simpler model that reflects a single timepoint. Specifically, we will use a one-way ANOVA with three groups (one for each treatment arm) modelling the change from baseline in each of our three measurements. We will additionally assume a two-sided alpha of 0.05. The hypothesis tested from this model will be any difference in mean change from baseline between the three treatment groups.

The literature suggests that the average NOx level in stable sickle cell patients is 25.5, with a standard deviation of 2.2. We assume that both groups start out with this mean and that the placebo group maintains this level across the length of the study. Based on preliminary findings, we expect a minimum increase of 1.75 for the high dose in the mean change from baseline NOx and the low dose to have a related 1.375 increase. If we assume that the variance is equivalent for the pre and post measurements, we can calculate the variance of the difference as the sum of the pre and post variances minus twice the covariance between pre and post measurements. Thus, our variance estimate depends greatly on the correlation between the pre and post measurements. Assuming a range of correlations (0.3, 0.5, and 0.7), we can then estimate the sample size we will need to detect the differences of 1.375 and 1.75 at 80% and 90% power. (See table below.)

Total sample sizes (for each age group) by power and correlation for NOx assuming a 1:1:1 randomization.

		Power	
		80%	90%
Correlation	0.7	27	33
	0.5	42	54

	0.3	57	72
--	-----	----	----

Given that the goal of this trial is exploratory, not confirmatory, we do not need to achieve a significant value on any specific hypothesis test. Additionally, a much larger treatment effect is anticipated, potentially giving us more power. Thus, a reasonable sample size to achieve our goals and provide us with a reasonable estimate, with the potential to see a significant effect is in the range of 48 total subjects in each age group. With the elimination of one dose of Arginine, the sample size of 16 adults per remaining treatment group will be used.

Insufficient data is available in the literature at this time to sufficiently estimate the expected within subject variability (at steady state of SCD) for the Gardos Channel Activity and erythrocyte density (MCHC >41) as measured by Advia. Sample size calculations would therefore be based on unfounded assumptions and are therefore not provided.

Since the rate of dropout cannot be estimated at this time, completion of the study will be monitored and dropouts will be replaced as they occur. This should pose no problem due to the relatively short duration of the trial. All available data on dropouts will be used in the analyses.

Although clinical events, such as vaso-occlusive pain episodes will be analyzed secondarily in this trial, it is believed that enough information on these endpoints will be gathered to plan for an appropriately sized Phase III trial that would use a clinical endpoint in the primary hypothesis. Since all subjects must have had at least one vaso-occlusive pain event in the past year, it is estimated that for each age group, at least 24 events would occur. Although probably not enough to provide a confirmatory test of the effect of arginine on clinical outcomes, it should certainly be enough to provide planning estimates for the confirmatory trial.

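### The Section 12.1 sample-size table is presented as giving 80% and 90% power for the low-dose difference of 1.375, but its totals belong to a three-group omnibus test, and no power is given for low dose versus placebo, the only comparison still randomised.

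*Protocol*

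**What the plan says.** Section 12.1 sizes each age group separately. For simplicity it replaces the planned longitudinal analysis with a single-timepoint model: "we will use a one-way ANOVA with three groups (one for each treatment arm) modelling the change from baseline". The hypothesis is an omnibus one: "The hypothesis tested from this model will be any difference in mean change from baseline between the three treatment groups". The error rate is stated as "We will additionally assume a two-sided alpha of 0.05".

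The NOx inputs are a mean of 25.5 "with a standard deviation of 2.2", the assumption that "the placebo group maintains this level across the length of the study", and increases of 1.75 for the high dose and 1.375 for the low dose. Pre-post correlations of 0.3, 0.5 and 0.7 are considered. The section then says "we can then estimate the sample size we will need to detect the differences of 1.375 and 1.75 at 80% and 90% power". The tabulated totals per age group under 1:1:1 allocation, for 80%/90% power, are 27/33 at correlation 0.7, 42/54 at 0.5 and 57/72 at 0.3.

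On the amendment, the section says "With this amendment, subjects are now only randomized to placebo and low dose arginine" and, on size, "With the elimination of one dose of Arginine, the sample size of 16 adults per remaining treatment group will be used". Section 7.2 adds that the 16 children and 14 adults already randomised to the high dose stay in the evaluation. No power is given for low dose versus placebo.

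**The concern.** An omnibus F test can have 80% power while one of its pairwise contrasts has far less. Describing the totals as the size needed to detect each named difference therefore attaches 80% and 90% to the low-dose difference without any calculation behind it. Before the amendment this was loose wording about one of three comparisons. Once the high-dose arm closed, low dose versus placebo became the only comparison still being randomised, and the sentence and table were left as they were.

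What is at stake is interpretation. Section 12.4.2 says the results are meant to justify and size a phase III trial. A reader who believes that about 48 per age group gives roughly 80% to 90% power for 1.375 at correlation 0.5 could take a non-significant low-dose result as evidence of no effect. The sizing does not support that inference.

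**Working it through.** **Inputs, all from Section 12.1.** Single-measurement SD 2.2; pre-post correlation r = 0.7, 0.5, 0.3; placebo change 0; low dose 1.375; high dose 1.75 as printed; two-sided alpha 0.05; equal arms.

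**SD of change.** The section takes the sum of the pre and post variances minus twice the covariance, with equal variances. So SD = 2.2 × √(2(1 − r)) = 1.704, 2.200, 2.603.

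**Step 1: the plan's own table.** One-way ANOVA power comes from the noncentral F with 2 and 3n − 3 degrees of freedom and noncentrality λ = n × Σ(μᵢ − μ̄)² / SD². The smallest equal n per arm that reaches the target gives these totals (80%/90%):

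| r | Printed table | Means 0, 1.375, 1.75 | Means 0, 1.375, 2.75 |
|---|---|---|---|
| 0.7 | 27/33 | 54/69 | 27/33 |
| 0.5 | 42/54 | 87/114 | 42/54 |
| 0.3 | 57/72 | 120/156 | 57/72 |

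The printed effects do not give the printed totals. On those effects the table's totals have only 46% to 58% omnibus power. Several variants of the printed inputs also fail to reproduce the table: alpha 0.10 or 0.20, a baseline-adjusted SD, SD = 2.2√(1 − r), and two-sample t tests at 1.375 and 1.75. With placebo at 0 and low dose at 1.375, a search over the high-dose effect in steps of 0.01 reproduces all six cells only from 2.74 to 2.77. The value 2.75 is exactly twice 1.375.

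**Step 2: what drives the totals.** With means 0, 1.375, 2.75 the grand mean is (0 + 1.375 + 2.75)/3 = 1.375. The low-dose deviation is therefore 0, and Σ(μᵢ − μ̄)² = 1.375² + 0 + 1.375². All the noncentrality comes from high dose versus placebo. With the printed means the low dose does contribute, but those means do not produce the table.

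**Step 3: low dose versus placebo under the same model.** Two-sided two-sample t test with noncentrality δ = 1.375 / (SD × √(2/n)) and 2n − 2 degrees of freedom. At n = 16 and r = 0.5, SE = 2.200 × √(2/16) = 0.778 and δ = 1.375/0.778 = 1.77, which gives power 40.2%.

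| | r = 0.7 | r = 0.5 | r = 0.3 |
|---|---|---|---|
| Power at the table's 80% total (9, 14, 19 per arm) | 36.3% | 35.7% | 35.4% |
| Power at the table's 90% total (11, 18, 24 per arm) | 43.7% | 44.5% | 43.3% |
| Power at 16 per arm | 59.8% | 40.2% | 30.4% |
| Per arm needed for 80%/90% | 26/34 | 42/55 | 58/77 |
| Difference detectable with 80% power, 16 per arm | 1.74 | 2.25 | 2.66 |

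Pooling the error over three arms of 16 adds about one point or less (60.8%, 40.9%, 31.0%). None of these figures uses the high-dose effect, so correcting 1.75 to any other value leaves them unchanged.

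**Step 4: baseline adjustment.** The planned analysis adjusts for baseline. At one visit the SD becomes 2.2 × √(1 − r²) = 1.571, 1.905, 2.099, and power at 16 per arm is about 67%, 51% and 43%.

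**Step 5: repeated visits, on assumptions the protocol does not state.** NOx is scheduled at five on-treatment visits (weeks 1, 2, 4, 8, 12; Section 7.2.2). Suppose every pair of visits has correlation r and the effect is constant from week 1. The baseline-adjusted mean of five visits then has variance 2.2² × [(1 + 4r)/5 − r²], SD 1.143, 1.302, 1.302, and power about 91%, 82% and 82%. Correlation that decays over time, or a later onset of effect, would lower these figures.

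**The case against.** The strongest reply is that the trial does not depend on this power. Section 12.1 states the omnibus hypothesis openly and heads the table with its 1:1:1 allocation. It says that no specific test has to reach significance and expects an effect larger than the planning minimum. Sections 12.3.3 and 12.4.2 call the analyses descriptive. No rule makes a non-significant low-dose result count against phase III. All of this stands, and it lowers the severity. It does not make the sentence about detecting 1.375 true. The larger anticipated effect is given no value, and at r = 0.5 the detectable difference of 2.25 is about 1.6 times the planned low-dose effect (2.25/1.375).

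The second reply is that the one-visit change score is a deliberate simplification. That also stands. A reader might infer from the 60%, 40% and 30% that these are the trial's real power, but the documents do not support that reading. The planned model adjusts for baseline and uses all visits, and under favourable assumptions it reaches about 80% to 90%. The low figures show only that the printed claim fails under the model the section chose.

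A reader might also infer that 1.75 is a proven misprint for 2.75. The arithmetic points that way, but the documents do not say so. Nor is the omnibus p-value the planned report: the ANOVA is a sizing device, and Section 12.4.2 concentrates on estimating treatment relationships over time.

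**Conclusion.** The concern holds as a misstatement of power. The Section 12.1 totals are for a three-arm omnibus test, do not follow from the printed high-dose effect, and are not the size needed to detect 1.375. Under the section's own inputs and model, low dose versus placebo falls 44 to 47 points short of the stated power in every cell. At 16 per arm it has 60%, 40% or 30% power, depending on correlation.

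This rests on SD 2.2, the three stated correlations, a single timepoint, an unadjusted change score, and 16 evaluable patients per arm (dropouts are to be replaced). It does not establish that the planned analysis is underpowered, because the protocol gives neither the between-visit correlation nor the time course of effect on which that depends. Nor does it show that the trial should be larger. Severity is moderate: the exploratory aim is explicit, but the power statement was left unrevised when the amendment changed the comparison.

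**What to change.** No added patients. In Section 12.1:

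- Label the table as the original three-arm omnibus sizing and reconcile the high-dose effect with it. Either the effect or the totals must change, and the sponsor should say which was intended.
- State that the table is not the power to detect 1.375.
- Name low dose versus placebo within age group as the comparison still randomised. Print its power at 16 per arm under the same model (60%, 40%, 30% at correlation 0.7, 0.5, 0.3) and the difference detectable with 80% power (1.74, 2.25, 2.66).
- Add that single-visit baseline adjustment gives about 67%, 51% and 43%, and that the repeated-measures model may give more, depending on between-visit correlation and a constant effect. If the sponsor holds data on these, state the assumed values and the resulting power.
- Commit to reporting the low-dose-versus-placebo estimate from the planned model with its 95% confidence interval, so that a non-significant result is not read as evidence of no effect.

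The cost is a few sentences and a less favourable stated power. Enrolment, visits and the planned model stay as they are.
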